5.5.2 Definition of Serious Adverse Events (SAEs)

An adverse event is considered "serious" if, in the view of either the investigator or sponsor, it results in any of the following outcomes:

- Results in death,
- Is life threatening (an adverse event is considered "life-threatening" if, in the view of either the investigator or sponsor, its occurrence places the subject at immediate risk of death. It does not include an adverse event that, had it occurred in a more severe form, might have caused death),
- Results in persistent or significant disability/incapacity or substantial disruption of the ability to conduct normal life functions,
- Results in congenital anomaly or birth defect,

- Requires inpatient hospitalization or leads to prolongation of hospitalization (hospitalization for treatment/observation/examination caused by AE is to be considered as serious).
- Other medically important events.

Medical and scientific judgment should be exercised in deciding whether expedited reporting is appropriate in other situations, such as important medical events that may not be immediately life-threatening or result in death or hospitalization but may jeopardize the subject or may require intervention to prevent 1 of the other outcomes listed in the definition above. These events, including those that may result in disability/incapacity, should also usually be considered serious. Examples of such events are intensive treatment in an emergency room or at home for allergic bronchospasm; blood dyscrasias or convulsions that do not result in hospitalization; or development of drug dependency or drug abuse. Additionally, Astellas requests that all medical events listed in [Appendix 2](#) (Liver Safety Monitoring and Assessment) be reported by the Investigator as SAEs, even if none of the above criteria apply.

Safety events of interest (“Special Situations”) on the Sponsor medicinal products administered to the subject as part of the study (e.g., study drug, comparator, background therapy) that may require expedited reporting and/or safety evaluation include, but are not limited to:

- Overdose of the medicinal product
- Suspected abuse/misuse of the medicinal product
- Inadvertent or accidental exposure to the medicinal product
- Medication error involving the medicinal product (with or without subject/patient exposure to the sponsor medicinal product, e.g., name confusion).
- Drug-drug interactions

Concerning other special situations: lack of efficacy is not to be recorded or reported as an AE in this study, as the study end point monitors the effect of the study drug. Due to the method of oral administration of roxadustat the risk of transmission of infectious agents is limited for which these events do not need to be reported. Off-label use of roxadustat can be excluded for reporting as the product is under development.

All of the events of interest noted above should be recorded on a SAE Worksheet and within the timelines of reporting SAEs, thus within 24 hours of becoming aware of this event. The above special situations will not be captured on the AE form in the eCRF, instead they will be captured in the dosing and accountability forms within the eCRF.

If special situation also induces an adverse event, this AE should be recorded on the AE page of the eCRF. Note, the seriousness criteria described in this section do not apply for the above special situations themselves but only for their potentially induced adverse events. This means that on the SAE Worksheet the seriousness criteria for a special situation only should be left blank.

The sponsor has a list of events that they classify as “always serious” events. If an adverse event is reported that is considered to be an event per this classification as “always serious”, additional information on the event may be requested.

If a subject becomes pregnant during treatment, this should be reported as if it were a SAE. Refer to Section 5.5.8 Procedure in Case of Pregnancy.

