5.5.1 Definition of Adverse Events (AEs)

An adverse event (AE) is defined as any untoward medical occurrence in a subject administered a study drug or has undergone study procedures and which does not necessarily have a causal relationship with this treatment. An AE can therefore be any unintended sign (including an abnormal laboratory finding), symptom or disease temporally associated with the use of a medicinal (investigational) product, whether or not related to the medicinal (investigational) product.

Some countries may have additional local requirements for events that are required to be reported as AEs or in an expedited manner similar to an SAE. In these cases, it is the investigator's responsibility to ensure these AEs or other reporting requirements are followed and the information is appropriately recorded in the (e)CRF accordingly.

An abnormality identified during a medical test (e.g., laboratory parameter, vital sign, ECG data, physical exam) should be defined as an AE only if the abnormality meets 1 of the following criteria:

- Induces clinical signs or symptoms
- Requires active intervention
- Requires interruption or discontinuation of study medication
- The abnormality or investigational value is clinically significant in the opinion of the investigator.

AEs present prior to study drug administration will be considered as 'non-treatment emergent'. Baseline conditions that worsen during the study will be recorded as adverse events. Adverse events with a start date after subjects have completed EOS procedures will not be captured.

For AEs that resolve during the subject's participation in the study, a resolution date will be documented in the eCRF. AEs will be followed until resolved, stable, or until the subject's last study visit or lost to follow up. AEs ongoing at the EOS visit will be followed up for as long as necessary to adequately evaluate the subject's safety or until the event stabilizes.

Data to be recorded in the eCRF include a description of the event, date of onset, onset status (onset before/after first dose of double-blind medication), end of the event, severity, SAE, seriousness criteria, action with respect to study medication, treatment required, relationship to study drug and outcome of the event.

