The study period during which all AEs and SAEs must be reported begins after informed consent is obtained and ends 28 days after the last dose of study drug or through to EOS, except for pregnancy reporting [see Section 5.5.8]. For subjects that continue into the post study follow-up period, SAEs, cardiovascular and thromboembolic AEs will be captured until their projected date of completion of the follow-up period (i.e., projected week 108) or until the last subject randomized reaches EOS, whichever comes first.

During the AE reporting period, study site personnel will query each subject at each visit to actively solicit any AE occurring since the previous visit. All AEs will be collected in response to a general question about the subject's well-being and any possible changes from the BL or previous visit, but shall not be specifically solicited. There will be no directed questioning for any specific AE. This does not preclude the site from collecting and recording any AEs reported by the subject to site personnel at any other time.

Whenever possible, diagnoses should be recorded when signs and symptoms are due to a common etiology, as determined by qualified medical study staff. New indications for medications started after informed consent until 28 days after the last dose of study drug or through to EOS visit, will be recorded as AEs; recurrence or worsening of medical history problems requiring new or changes in concomitant medication, will also be recorded as AEs. Abnormal, clinically significant laboratory results, physical examination findings, and ECGs will be recorded as AEs if they are deemed by the investigator to meet criteria.

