6.2.1.3 Time to occurrence of a TEAE (by type of AE group)

TEAEs are also classified into a number of groups depending on the following factors:

- Serious TEAEs
- Death during the Safety Emergent Period
- Any deaths (during the 24-month period)
- Related Serious TEAEs
- TEAEs Leading to permanent Discontinuation of the study drug
- TEAEs NCI CTC Grade 3 or Higher
- MedDRA System Organ Class (SOC)

The time to occurrence for a subject with a TEAE for a given type (except any deaths) will be calculated (in years) as:

$(\text{First TEAE date of the given type during the Safety Emergent Period} - \text{Analysis date of first dose intake} + 1) / 365.25$

With 'Analysis date of first dose intake' defined in Section [6.5.4](#) All adverse events collected during the Safety Emergent Period will be counted as TEAE, irrespective of use of rescue therapy.

Subjects who have not experienced a TEAE for that given type will be censored; the subject will be censored and the time to censoring for these subjects will be calculated (in years) as:

$(\text{Date of End of Safety Emergent Period} - \text{Analysis date of first dose intake} + 1) / 365.25$

With date of end of Safety Emergent Period defined in Section [7.11.5](#)

For any deaths during the 24-month period (including those occurring during the Post-Study Follow Up Period), time to occurrence for a subject who died during study / post study follow up) will be calculated (in years) as:

$[\text{End date for corresponding Fatal AE} - \text{Analysis date of first dose intake} + 1] / 365.25$

With 'End date for corresponding Fatal AE' which cover both study and post-study FU occurring up to Day 760 (i.e., month 24 + one month follow up + 3 days window as per protocol).

Subjects who have not died; the subject will be censored and the time to censoring for these subjects will be calculated (in years) as:

$\text{Minimum between } [\text{Day 760 and Max (Date of last known date when subject alive (End of Post-study FU), Date of last contact (Post study FU visit/call), Date of last Study evaluation (EOS form))} - \text{Analysis date of first dose intake} + 1] / 365.25$

Additional analyses censoring data post dialysis:

Time to occurrence with censoring all data at the initiation of permanent dialysis will be calculated as above where events occurring after initiation of dialysis will not be considered.

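### The protocol can be read both ways on whether worsening anemia that needs rescue is an adverse event, and the SAP has no anemia-excluded version of the pooled safety comparisons

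*Protocol*

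**What the plan says.** **Instructions that point toward recording (Protocol 5.5.1).** "Baseline conditions that worsen during the study will be recorded as adverse events". An abnormal test result can be an AE only if it meets one of four criteria, one of which is "Requires active intervention". The section also lists as AEs "New indications for medications started after informed consent until 28 days after the last dose of study drug" (or through the EOS visit), and says that "recurrence or worsening of medical history problems requiring new or changes in concomitant medication, will also be recorded as AEs". None of these sentences mentions anemia or rescue.

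**Instructions that point away from recording (Protocol 5.5.2).** Under special situations, "lack of efficacy is not to be recorded or reported as an AE in this study", with the reason that the study endpoint already monitors the drug's effect. A later paragraph adds: "If special situation also induces an adverse event, this AE should be recorded on the AE page of the eCRF". The term lack of efficacy is not defined.

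**What the SAP does with the data.** SAP 6.2.1.3: "All adverse events collected during the Safety Emergent Period will be counted as TEAE, irrespective of use of rescue therapy". SAP 7.5.1.1 to 7.5.1.3 give the overview, the SOC and preferred-term tables and the event rates. SAP 7.5.1.4 gives Cox hazard ratios for serious TEAEs, Grade 3 or higher TEAEs, each SOC above 10%, deaths and other categories. SAP 7.5.1.5 and 7.5.1.6 add subgroup, dialysis-censored and last-dose-plus-7-days versions. None of these excludes anemia terms. SAP 6.2.1.2 states that no SMQs will be run. Protocol 7.5.5 allows optional analyses by ESA rescue and without CV events after rescue, but does not address anemia recorded as an AE.

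**The concern.** Take a subject whose CKD anemia worsens and who receives ESA, IV iron or a transfusion. One site can treat this as a baseline condition that worsened and enter an AE. Another can treat it as lack of efficacy and enter nothing. An admission for anemia, a category that SAP 6.1.3.6 foresees, could likewise become a serious AE or be left off the AE page.

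These events should not fall evenly. The plan expects far more non-response on placebo and tests superiority of roxadustat on rescue (SAP Table 16). Any recording of efficacy failure therefore adds relatively more events on placebo. This does not need sites to treat the arms differently: under blinding the recording share can be equal, and the imbalance comes from the number of failures. What is at stake is how the pooled ratios are read. A hazard ratio below 1 for serious or Grade 3 or higher TEAEs could partly reflect untreated anemia on placebo, and a modest excess of other events on roxadustat could be offset.

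**Working it through.** **1. The passages side by side.**
- 5.5.1, worsening baseline conditions: applies to anemia on its face and carries no exemption. This is the strongest text for recording.
- 5.5.1, worsening medical history problems: weaker, because Protocol 5.2.2 defines medical history as excluding the target disease.
- 5.5.1, new indications: also weak, since anemia is not a new indication in this population.
- 5.5.1, active intervention: a necessary condition for a test abnormality, applied with investigator judgement. It permits recording but does not compel it.
- 5.5.2, lack of efficacy: against recording, but silent on whether worsening that needs rescue is included.
- 5.5.2, AE induced by a special situation: could return the event to the AE page.

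The conflict rests on the first and fifth items, and the sixth does not settle it.

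**2. The plan's own figure.** Protocol 7.1 states more than 95% power with 300 and 150 subjects, response 65% and 25%, two-sided 0.05 (SAP 4). A two-proportion calculation gives more than 0.9999, so the statement holds. Planned non-response is 35% × 300 = 105 on roxadustat and 75% × 150 = 112.5 on placebo, a gap of 40 percentage points.

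**3. Illustration of size, with no true safety difference.** Let q be planned non-response (0.35 or 0.75), b the background risk of the AE category, r the share of non-responders whose anemia worsens and needs rescue, and s the share of those events that are both recorded and meet the category. Only q comes from the documents. The values of b, r and s are assumptions, taken as equal in both arms.

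Risk = 1 − (1 − b)(1 − q·r·s). Apparent HR = ln(1 − risk on roxadustat) / ln(1 − risk on placebo).

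Example with b = 0.20, r = 0.2, s = 0.5:
- roxadustat: 1 − 0.80 × (1 − 0.035) = 0.228
- placebo: 1 − 0.80 × (1 − 0.075) = 0.260
- HR = ln(0.772)/ln(0.740) = 0.86

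Range over r = 0.2 to 0.5 and s = 0.25 to 1.0:

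| b | Apparent HR | Risk difference (points) |
|---|---|---|
| 0.20 | 0.92 to 0.60 | −1.6 to −16.0 |
| 0.40 | 0.96 to 0.72 | −1.2 to −12.0 |
| 0.60 | 0.98 to 0.80 | −0.8 to −8.0 |
| 0.85 | 0.99 to 0.88 | −0.3 to −3.0 |

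If few events qualify (s = 0.05 to 0.10) at b = 0.20, the range is 0.98 (r = 0.2, s = 0.05: ln(0.7972)/ln(0.7940)) to 0.92 (r = 0.5, s = 0.10: ln(0.7860)/ln(0.7700)). If nothing is recorded, s = 0 and HR = 1.00.

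**4. Offsetting.** Give roxadustat a true HR of 1.2 with b = 0.20, r = 0.2, s = 0.5. Its risk is 1 − 0.80^1.2 × 0.965 = 0.262, against 0.260 on placebo, and the apparent HR is 1.01.

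Non-response is only a stand-in for efficacy failure. The EU endpoint covers 24 weeks and counts discontinued subjects as non-responders, while the safety period runs to 28 days after the last dose.

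**The case against.** The case against is substantial.

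- **A specific rule may override general ones.** The lack-of-efficacy sentence is explicit for this study and gives its reason, and 5.5.1 never names anemia. A coherent reading exists: failure to respond is not an AE, but its clinical consequences are. This stands as a possible reading, but the protocol does not state it, and sites cannot be assumed to have reached it.
- **Anemia would be visible.** SAP 7.5.1.2 tabulates overall, serious and Grade 3 or higher TEAEs by SOC and preferred term. SAP 7.5.1.4 gives hazard ratios by SOC, and those for other SOCs contain no anemia terms. Anemia admissions are described separately. Adjudicated MACE and MACE+ are analyzed in a separate pooled program. This stands and narrows the exposure to the pooled any-category summaries, together with the SOC holding the anemia terms. Visibility does not supply a pooled hazard ratio without those terms.
- **Few rescues may qualify as serious or Grade 3 or higher.** This stands. Outpatient IV iron or an ESA course need not be either.

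Two further inferences are tempting but unsupported. A reader might take the criterion "Requires interruption or discontinuation of study medication" to make every dosing stop for Hb of 13.0 g/dL or above an AE. It is an only-if condition subject to judgement, so it does not. A reader might also extend the point to AEs leading to discontinuation in general. The SAP category is permanent discontinuation. Under Protocol 5.1.5 one ESA course only interrupts dosing, IV iron and transfusion allow study drug to continue, and only a third ESA course ends treatment. SAP 7.2.1 also plots lack of efficacy as its own discontinuation reason.

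**Conclusion.** The recording instructions are open to opposite readings for worsening anemia that needs rescue, and the SAP neither resolves this nor isolates its effect. The consequence is a risk whose direction favors roxadustat, provided that rescue among non-responders and recording are similar across arms. Its size is unknown. The illustrative range, from close to 1 down to 0.60, depends on assumed background, rescue and recording shares. The overall TEAE proportion would barely move if most subjects have a TEAE anyway. Serious and Grade 3 or higher categories could move more, but only as far as anemia events meet those criteria.

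A reader might infer that placebo efficacy failures did enter the safety tables and distorted them site by site. The documents do not support that. They contain no recording practice and no observed rates.

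**What to change.** 1. **Protocol 5.5.1 and 5.5.2.** Reconcile the sentences on worsening baseline conditions, worsening history, test abnormalities and lack of efficacy, so that sites follow one recording instruction for worsening anemia that needs rescue. The instruction should not drop events that meet a seriousness criterion. This changes no dosing or rescue rule.
2. **SAP 7.5.1.1 to 7.5.1.4.** Pre-specify a sensitivity repeat of the overall, serious and Grade 3 or higher TEAE summaries, and of the Cox hazard ratios for serious and Grade 3 or higher TEAEs, excluding a list of anemia and low-Hb preferred terms. Fix the list before unblinding and show the results beside the unrestricted analyses, which stay as planned.

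The cost is a short protocol clarification, one extra table set and a preferred-term list. The second step matters most in practice: it works on data already collected and separates recorded anemia from other events whichever instruction sites followed.

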5.5.3 Criteria for Causal Relationship to the Study Drug

Adverse events that fall under either "Possible" or "Probable" should be defined as "adverse events whose relationship to the study drugs could not be ruled out".

Table 6 Criteria for Causal Relationship to Study Drug

Causal relationship to the study drug	Criteria for causal relationship
Not Related	A clinical event, including laboratory test abnormality, with a temporal relationship to drug administration which makes a causal relationship improbable, and/or in which other drugs, chemicals or underlying disease provide plausible explanations.
Possible	A clinical event, including laboratory test abnormality, with a reasonable time sequence to administration of the drug, but which could also be explained by concurrent disease or other drugs or chemicals. Information on drug withdrawal may be lacking or unclear.
Probable	A clinical event, including laboratory test abnormality, with a reasonable time sequence to administration of the drug, unlikely to be attributed to concurrent disease or other drugs or chemicals, and which follows a clinically reasonable response on re-administration (rechallenge) or withdrawal (dechallenge).

5.5.4 Criteria for Defining the Severity of an Adverse Event

Severity of AEs will be graded according to National Cancer Institute - Common Terminology Criteria for Adverse Events (NCI-CTCAE) Version 4.03. For terms not specified as part of NCI-CTCAE Version 4.03, the following guideline should be used to determine grade:

Table 7 Criteria for Defining the Severity of an Adverse Event

Grade	Description
1 - Mild	Mild; asymptomatic or mild symptoms, clinical or diagnostic observations only; intervention not indicated.
2 - Moderate	Moderate; minimal, local or non-invasive intervention indicated.
3 - Severe	Severe or medically significant but not immediately life-threatening; hospitalization or prolongation of hospitalization indicated.
4 – Life threatening	Life-threatening consequences; urgent intervention indicated.
5 - Death	Death related to AE.

5.5.5 Reporting of Serious Adverse Events (SAEs)

In the case of a SAE, the investigator must contact the delegated CRO by telephone or fax immediately (within 24 hours of awareness).

The investigator should complete and submit a SAE Worksheet containing all information that is required by the Regulatory Authorities to delegated CRO by fax immediately (within 24 hours of awareness). Toll free fax number for each country is provided on the fax coversheet of the SAE Worksheet. In case of fax failure the SAE Worksheet should be emailed to the delegated CRO.

If the faxing of a SAE Worksheet is not possible or is not possible within 24 hours, the drug safety contact should be informed by phone.

The contact details of the delegated CROs are:

[REDACTED]

[REDACTED]

[REDACTED]

If there are any questions, or if clarification is needed regarding the SAE, please contact the Sponsor's Medical Monitor or his/her designee (see Section II Contact Details of Key Sponsor's Personnel).

After checking for completeness and accuracy, the delegated CRO will send the SAE Worksheet and (when present) source documents (within 24 hours of receipt) to the Sponsor.

Follow-up information for the event should be sent promptly (preferable within 7 days of the initial notification).

Full details of the SAE should also be recorded on the medical records and in the eCRF. The investigator must ensure that the information on the SAE Worksheet matches the information on the AE pages within the eCRF.

The following minimum information is required to be completed on the SAE form:

- ISN/Study number
- Subject number, sex and age
- Date of report
- A description of the SAE (event, seriousness of the event)
- Causal relationship to the study drug

All SAEs, including death, should be reported up to EOS visit or up to 28 days after the last intake of study medication, whichever is last. Any hospitalizations and/or death during the Post-Study follow-up period should also be reported as an SAE.

The sponsor or sponsor's designee will submit expedited safety reports (i.e., IND Safety Reports) to the regulatory agencies as necessary, and will inform the investigators of such regulatory reports. Investigators must submit safety reports as required by their IRB/IEC within timelines set by regional regulations (i.e., EU). Documentation of the submission to and receipt by the IRB/IEC of expedited safety reports should be retained by the site.

The delegated CRO will notify all investigators responsible for ongoing clinical studies with the study drug of all SAEs which require submissions per local requirements of IRB/IEC/head of the study site.

The investigators should provide written documentation of IRB/IEC notification for each report to the Sponsor.

You may contact the sponsor's Medical Monitor for any other problem related to the safety, welfare, or rights of the study subject.

For SUSARs from a blinded trial, unblinded Council for International Organizations of Medical Sciences-I report will be submitted to the authorities and IRB/IEC where required.

